## LIST OF ABBREVIATIONS

AE	Adverse Event/Adverse Experience
ALT	Alanine Transaminase
AST	Aspartate Aminotransferase
BSAP	Bone-specific alkaline phosphatase
BUN	Blood Urea Nitrogen
CBC	Complete Blood Count
CDG	Congenital Disorder of Glycosylation
CFR	Code of Federal Regulations
Cl	Chloride
CNS	Central Nervous System
CO2	Carbon Dioxide
CRF	Case Report Form
CTCAE	Common Terminology Criteria for Adverse Events
CTX	Carboxy-terminal collagen crosslinks
DSMB	Data and Safety Monitoring Board
EMR	Electronic Medical Record
FDA	Food and Drug Administration
GCP	Good Clinical Practice
Hct	Hematocrit
Hgb	Hemoglobin
HIPAA	Health Insurance Portability and Accountability Act
ICARS	The International Cooperative Ataxia Rating Scale
IND	Investigational New Drug Application
IRB	Institutional Review Board
K	Potassium
LFT	Liver Function Tests
MCH	Mean Corpuscular Hemoglobin
MCHC	Mean Corpuscular Hemoglobin Concentration
MCV	Mean Corpuscular Volume
MVRD	Midsagittal Vermis Relative Diameter
Na	Sodium
NPCRS	Nijmegen Pediatric CDG Rating Scale
PTH	Parathyroid Hormone
pCO2	Partial Pressure of Carbon Dioxide
PHI	Protected Health Information
PI	Principal Investigator
Plt	Platelet
PMM2	Phosphomannomutase deficiency
pO2	Partial Pressure of Oxygen
PRO	Patient Reported Outcome
SAE	Serious Adverse Event/Serious Adverse Experience
SOP	Standard Operating Procedure
VBG	Venous Blood Gas

## Study Summary

Title	A randomized, double-blind, placebo-controlled study evaluating Acetazolamide efficacy in ataxia in PMM2-CDG
Running Title	Acetazolamide Trial in PMM2-CDG
Protocol Number	20-000634
Methodology	Randomized, double-blind, placebo-controlled, parallel
Overall Study Duration	1 years (52 weeks)
Subject Participation Duration	Treatment period = 6 months (26 weeks); Open Label period = 6 additional months (26 weeks); Total of 1 year (52 weeks)
Single or Multi-Site	Multicenter – 3 sites (Seattle Children’s Hospital, Children’s Hospital of Philadelphia, Mayo Clinic)
Objectives	
Objective 1 (Primary): To determine the efficacy of acetazolamide in improving ataxia in patients with PMM2-CDG.
 
Objective 2 (Secondary): To evaluate for any adverse events related to longer term acetazolamide administration.
 
Objective 3 (Secondary): To examine the effect of acetazolamide on PMM2 biomarkers including carbohydrate deficient transferrin results, electrolytes (Na, K, Cl, CO2), VBG (pH, pCO2, PO2, CO2 excess) or bicarbonate/CO2, liver function tests (AST, ALT, GGT, indirect and direct bilirubin, total protein, albumin, alkaline phosphatase), kidney function tests (BUN, Creatinine, Urinalysis, urine calcium/creatinine ratio, urine protein/creatinine ratio), growth (height, weight, head circumference), vital signs (blood pressure, respiratory rate, heart rate), PROMIS scores, dysarthria using the PATA score, and NPCRS score.
 
Objective 4 (Secondary): To explore characteristics of individuals with PMM2-CDG who do not respond to acetazolamide.

Number of Subjects	26 total subjects

Diagnosis and Main Inclusion/Exclusion Criteria	
Inclusion criteria:
 
 
1. Biallelic pathogenic or likely pathogenic variants in PMM2 OR Biallelic variants of uncertain significance, pathogenic, or likely pathogenic variants in PMM2 AND Enzymatic confirmation of PMM2 enzyme deficiency
 
2. Age <math>\geq 4</math> years old, and
 
3. Affected with ataxia evidenced by mini International Cooperative Ataxia Rating Scale (Mini-ICARS) score <math>>0</math> at baseline.
 
 
Exclusion criteria:
 
 
1. Hepatic impairment defined as AST/ALT <math>>3.0 - 5.0 \times</math> ULN if baseline was normal; <math>>3.0 - 5.0 \times</math> baseline if baseline was abnormal
 
2. Renal impairment defined as serum creatinine 1.5-1.9 times ULN for age OR <math>\geq 26.5 \text{ umol/l}</math> increase from ULN for age
 
3. Hypokalemia
 
4. Hyponatremia
 
5. Hyperchloremic acidosis
 
6. Adrenal insufficiency
 
7. Hypersensitivity to acetazolamide
 
8. Hypersensitivity to any of the components of the placebo
 
9. History of treatment with experimental drug within 28 days of Visit 1
 
10. Currently taking Mecamylamine, Sodium Phosphates, Salicylates, Mefloquine, Methenamine and other Carbonic Anhydrase Inhibitors
 
11. Weight <math><10 \text{ kg}</math>
 

Study Product, Dose, Route, Regimen	
Acetazolamide or Placebo
 
Acetazolamide capsules <math>\leq 30 \text{ mg/kg/day}</math> divided BID or matching placebo, divided BID daily, by mouth.
 
Due to the potential of subject intolerance, we will start patients on a lower dose divided BID and titrate up in a stepwise manner per table 1 if well tolerated with no AEs or abnormal pH. If the pH is <math><7.3</math> and/or bicarbonate <math><21</math>, the dose will be reduced by <math>7\text{mg/kg/day}</math>.

Duration of Administration	12 months (52 weeks) total, 6 months (26 weeks) blinded, 6 months (26 weeks) open label extension
Reference therapy	Placebo
Statistical Methodology	
The primary analysis will be conducted using the full analysis set, defined as all randomized patients who complete the baseline and 6-month visits. The between-arm mean difference in the change in Mini-ICARS score from baseline to 6 months will be evaluated via a two-sample t-test. The primary analysis will include all patients with a baseline and 6-month Mini-ICARS score.

## 1 Introduction

This document is a protocol for a human research study. This study will be carried out as described in this protocol and comply with all principles of Good Clinical Practice (GCP), as described in the United States Code of Federal Regulation (CFR) 21 Parts 11, 50, 54, 56, and 312 and the appropriate International Conference on Harmonization guidance documents.

### 1.1 Background

Phosphomannomutase deficiency, also known as PMM2-CDG, is the most common congenital disorder of glycosylation (CDG), with over 700 reported cases worldwide. It is an autosomal recessive disorder caused by biallelic pathogenic variants in the *PMM2* gene (Grunewald et al. 2002, Jaeken et al. 1980, 2014). Clinically, PMM2-CDG is characterized by multisystemic severe disease and cerebellar atrophy in infancy, neurologic disease including ataxia and developmental delay in childhood, and/or stable intellectual disability in adulthood (Freeze et al. 2012, Grunewald et al. 2009).

Cerebellar atrophy and cerebellar motor symptoms are common in patients with PMM2-CDG, typically more severe in the first decade of life (Barone et al. 2014, 2015, DeDiego et al. 2017). On a quality of life questionnaire administered to all families attending the 2019 World CDG conference, ataxia was identified as a major symptom impacting daily life in all age groups (unpublished data). Cerebellar dysfunction is a major cause of long-term disability, loss of autonomy, and limitations in daily life for patients with PMM2-CDG.

The International Cooperative Ataxia Rating Scale (ICARS) is a scoring system that has been validated to assess the severity of ataxia symptoms in children and adults with PMM2-CDG. (Serrano et al. 2015, 2017). The ICARS assessment was validated against cerebellar atrophy as calculated by the midsagittal vermis relative diameter (MVRD) on MRI (i.e., using a midsagittal section and measuring total posterior cranial fossa diameter in a linear segment from the posterior commissura to the opisthium and the largest sagittal diameter of the cerebellum parallel to the previous linear segment. The ratio of the cerebellum diameter over the total posterior cranial fossa diameter was used (Serrano et al. 2015)). ICARS showed significant negative correlation with MVRD ( $r_s = -0.87$ ,  $p = 0.003$ ).

Ataxia symptoms and stroke like episodes in CACNA1A-related disorder, a genetic channelopathy, are attributable to gain-of-function effects on channel gating in the  $\text{Ca}_v2.1$  channel. Deficient N-glycosylation of  $\text{Ca}_v2.1$  induce a similar gain-of-function effect on this channel (Izquierdo-Serra et al. 2018). Lowering of intracellular pH and thus transmembrane potential may decrease the activation of  $\text{Ca}_v2.1$ . This, in turn, may restore the excitability and resting activity of neurons. Thus lowering the intracellular pH may ameliorate the cerebellar symptoms of PMM2-CDG, given the hypothesis that cerebellar symptoms are partially due to dysfunctional hypo glycosylated channels such as  $\text{Ca}_v2.1$ .

### 1.2 Investigational Agent

## Acetazolamide

Acetazolamide is a potent carbonic anhydrase inhibitor, effective in the control of fluid secretion, in the treatment of certain convulsive disorders, and in the promotion of diuresis in instances of abnormal fluid retention. Acetazolamide is not a mercurial diuretic. Rather, it is a nonbacteriostatic sulfonamide possessing a chemical structure and pharmacological activity distinctly different from the bacteriostatic sulfonamides. Acetazolamide is an enzyme inhibitor that acts specifically on carbonic anhydrase, the enzyme that catalyzes the reversible reaction involving the hydration of carbon dioxide and the dehydration of carbonic acid. Evidence seems to indicate that Acetazolamide has utility as an adjuvant in the treatment of certain dysfunctions of the central nervous system (CNS). Inhibition of carbonic anhydrase in this area appears to retard abnormal, paroxysmal, excessive discharge from CNS neurons. The diuretic effect of acetazolamide is due to its action in the kidney through the reversible reaction involving hydration of carbon dioxide and dehydration of carbonic acid. This reaction results in renal loss of HCO3 ions, which also carries out sodium, water, and potassium, leading to alkalinization of the urine and promotion of diuresis. Alteration in ammonia metabolism occurs due to increased reabsorption of ammonia by the renal tubules as a result of urinary alkalinization.

It is a white to faintly yellowish white crystalline, odorless powder, weakly acidic, very slightly soluble in water and slightly soluble in alcohol. The chemical name for acetazolamide is N-(5-Sulfamoyl-1,3,4-thiadiazol-2yl)-acetamide. As a carbonic anhydrase inhibitor that changes the intracellular pH, acetazolamide affects the transmembrane potential and conductance of potassium and calcium channels (Bain et al. 1992, Sappey-Marinier et al. 1999). While it has been studied more extensively in adults, it has been safely administered to children for a variety of indications at doses that range from 4 mg/kg/day to the lower of 100 mg/kg/day or 4000 mg/day (Moffett et al. 2007, Distelmaier et al. 2006, Hacifazlioglu et al. 2012, Ko et al. 2010, Park et al. 2014, Per et al. 2013, Rangwala et al. 2007, Reiss et al. 1996, Soler et al. 1998, Spennato et al. 2011, Standridge et al. 2010).

Acetazolamide is an FDA-approved drug for adults for treatment of glaucoma, epilepsy, altitude sickness, and edema. FDA approved doses are in adults 250 to 1000 mg/day divided once to four times daily. A documented off-label use is for treatment of familial periodic paralysis. While the regular-release capsule is not FDA approved in children, it is used commonly in clinical practice and recommended doses have been established in children for management of glaucoma and seizures, reversal of metabolic alkalosis, and prevention and treatment of altitude sickness at 10-30 mg/kg/day given in one to four divided doses. The extended released capsule is FDA-approved in children with a max dose of 30 mg/kg/day or 1000 mg/day (Acetazolamide, 2020).

Acetazolamide is contraindicated in cases of marked liver disease or dysfunction and in patients with cirrhosis because of the risk of development of hepatic encephalopathy and electrolyte imbalance. It is also contraindicated in patients with severe renal disease as it may potentiate acidosis and may cause CNS adverse effects in dialysis patients. It is contraindicated for individuals with carbonic anhydrase inhibitor hypersensitivity, sulfonamide hypersensitivity, electrolyte disturbances, and adrenal insufficiency. It has been reported to occasionally induce

bone marrow suppression and blood dyscrasias. It is an FDA pregnancy risk category C. These contraindications are reflected in our study exclusion criteria.

In this study, regular-release acetazolamide will be dispensed in compounded capsule and compounded liquid formulations.

### 1.3 Clinical Data to Date

Acetazolamide has previously been demonstrated to be efficacious in the treatment of ataxia symptoms in other genetic channelopathies including CACNA1A related disorder (Izquierdo-Serra et al. 2018). Acetazolamide has also been demonstrated to improve the cerebellar symptoms of PMM2-CDG over a six-month pilot study. This initial clinical trial in 24 patients ages 5 to 20 years (mean age  $12.3 \pm 4.5$  years, 9 females, 15 males) demonstrated that acetazolamide is well-tolerated and effective for motor cerebellar syndrome over six months in patients with PMM2-CDG (EudraCT 2017-000810-44). Subjects had statistically significant improvements in ICARS and Nijmegen Pediatric CDG Rating Scale (NPCRS) scores, and lower PATA rates. The PATA rate is the number of “pa – tas” an individual is able to speak in ten seconds. In this study, treatment with acetazolamide coincided with the gain of ability for some patients to sit and stand independently for a longer period of time, which caretakers rated to be an important clinical gain that significantly improved their quality of life and autonomy. Even patients with severe cerebellar atrophy (i.e., low MVRD) showed significant improvement in ICARS, demonstrating a potential therapeutic effect independent of structural cerebellar anomalies and atrophy. In fact, larger gains were observed in individuals with more severe ataxia demonstrated by higher baseline ICARS scores. There were no serious AEs related to the drug during the treatment. There was also no control group comparison, long term follow-up, nor ability to accurately titrate dose by mg/kg. An efficacious dosage of 22 mg/kg/day was established for optimal treatment response, although not all subjects were able to tolerate this dosage, leading to subject drop-out (Martinez-Monseny et al. 2019).

Nine of the 18 items on the ICARS showed consistent improvement in patients on acetazolamide (items 1, 3, 5, 6, 8, 10, 13, 14, 15) (Martinez-Monseny et. al. 2019). These nine items constitute the “Mini-ICARS.” Data from the initial validation study was reanalyzed looking at the items in the Mini-ICARS, and explored the internal consistency of the Mini-ICARS scale formed by the sum of the nine items in thirteen PMM2-patients. In collaboration with the authors of the initial clinical trial, we explored the internal consistency of the Mini-ICARS scale formed by the sum of the nine items in thirteen PMM2-patients and found that Cronbach’s alpha was very high at 0.96 by analyzing this subset data from the 2015 and 2017 ICARS validation studies. Additionally, the agreement of scores between three different evaluators of the Mini-ICARS from analysis of the 2015 and 2017 ICARS validation studies again showed a correlation very close to 1, demonstrating the Mini-ICARS is also valid in PMM2-CDG (Serrano et. al. 2015, 2017, personal communication). The Mini-ICARS comprehensively captures the areas of clinically significant improvement, while being much shorter to implement, decreasing the likelihood of testing fatigue and inability to complete clinical testing in subjects. Thus, we chose the Mini-ICARS to be the primary endpoint for this trial.

## 1.5 Risks and Benefits

### Risks

In general, acetazolamide is considered a safe drug. Per the package insert, severe adverse reactions that have been reported with administration of acetazolamide include seizures, muscle paralysis, hepatic necrosis, hepatic failure, hepatic encephalopathy, toxic epidermal necrosis, agranulocytosis, anaphylaxis, aplastic anemia, hemolytic anemia, Stevens-Johnson syndrome, pancytopenia, acute generalized exanthematous pustulosis, renal failure, and renal tubular obstruction. The incidence of each reaction is unknown. It is likely that individuals who have significant baseline allergy to acetazolamide and other components, hepatic dysfunction, blood dyscrasias, and/or renal dysfunction would be at higher risk for these severe reactions. Thus we are assessing for hepatic dysfunction, renal dysfunction, allergy, and blood dyscrasias at baseline and excluding individuals with significant disturbances in their laboratory assessments or have a history of allergy to the components of the therapeutic agent or placebo (as defined by the exclusion criteria below). We will monitor complete blood count (CBC), liver function tests (LFT), venous blood gas (VBG or bicarbonate/CO2), electrolytes, and creatinine, and urinalysis with urine creatinine, calcium, and protein at baseline and regularly throughout the study, and if any individual meets exclusion criteria at any point during the study, we will terminate their treatment. Patients may develop acidosis on acetazolamide therapy, which may lead to inability to continue the therapy longer or a decrease in dosage. Acetazolamide has been associated with growth suppression in pediatric patients, although not all individuals have been reported to have poor growth and the dosages associated with growth suppression have not been consistent. Growth has been reported to resume and improve after discontinuation of acetazolamide. We will monitor growth parameters (height, weight, head circumference) regularly throughout the study and tailor their management and continuation in the study on a case by case basis. We will monitor patients' acid/base status and titrate acetazolamide accordingly. We will also obtain a one-time measurement of acetazolamide serum concentration at steady state at the six-month visit.

Other less severe side effects may include depression, confusion, ataxia, hyperglycemia, hypoglycemia, glycosuria, jaundice, elevated hepatic enzymes, hyperuricemia, hemolysis, thrombocytopenia, leukopenia, hyperchloremia, hyponatremia, crystalluria, hypokalemia, nephrolithiasis, hematuria, myopia, growth inhibition, melena, dizziness, paresthesias, fatigue, drowsiness, malaise, headache, photosensitivity, urticaria, fever, polyuria, diarrhea, anorexia, xerostomia, nausea, vomiting, dysgeusia, flushing, tinnitus, and purpura. These symptoms are also all monitored during each visit by history and laboratory studies. Subjects may voluntarily withdraw at any time from the trial.

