### 3.7 Identification of Source Data

The following data will be collected:

- Date of visit
- Age at visit (Years, Months, Days)
- Vital signs: systolic and diastolic blood pressures (mmHg), heart rate (beats/minute), respiratory rate (breaths/minute), temperature (degrees C)
- Growth Data: length/height (cm), weight (kg), head circumference (cm)
- Physical Exam: brief neurologic exam, cardiovascular exam, abdominal exam, (HEENT) head ears eyes nose throat exam, dermatologic exam, pulmonary exam, musculoskeletal exam (Normal/Abnormal with text field to explain abnormality)
- PATA score
- AE and SAEs defined by the CTCAE version 5 (specific AE/SAE and date; see Appendix D)
- PROMIS Questionnaires (Appendix C)
- Mini-ICARS (Appendix B)
- NPCRS (Appendix A)
- Drug volume prescribed (ml/day or number of capsules/day)
- Laboratory values, normal ranges, and units: CBC (WBC, Hgb, Hct, Plt, % Neutrophils, % Lymphocytes, % Eosinophils, % Basophils, % Monocytes, % Bands, MCV, MCHC, MCH), electrolytes (Na, K, Cl, CO2), VBG (pH, pCO2, PO2, CO2, Base excess) or bicarbonate/CO2, liver function tests (AST, ALT, GGT, indirect and direct bilirubin, total protein, albumin, alkaline phosphatase), coagulation factors (prothrombin time, coagulation factor XI, and antithrombin), kidney function tests (BUN, Creatinine, Urinalysis, urine calcium/creatinine ratio, urine protein/creatinine ratio)
- BSAP, CTX, calcium, phosphorus, vitamin D, and PTH at baseline and visit 5.
- Plasma/Serum Acetazolamide level at visit 5.
- Physical therapy, Occupational therapy, Speech therapy, Feeding therapy – (yes/no if ongoing, number of sessions per month)
- Annual screening ophthalmological exam including intraocular pressure testing.

The following source data will be captured in supportive documentation (e.g. study source documents, EMR):

- Clinical interpretation of laboratory values
- Medication review and adherence
- Video of the Mini-ICARS assessment

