### Subject Identification:

Ethical and confidential research standards will be maintained. The minimum necessary protected health information will be used in study records. Computer records of data will be password protected behind institutional information technology security firewalls. All information will be treated with strict adherence to professional standards of confidentiality.

The following is a detailed list of study visits from screening to final follow-up and the required procedures/tests.

### 6.1 Visit 1 – Week 0

- Screening for eligibility
- Informed consent; no procedures will occur until informed consent and eligibility criteria are confirmed.
- Interview elements:
  - Medical history (past and current medical conditions, past surgical history)
  - Clinical history (history of present illness, any assessments)
  - Concomitant medication review
  - Ongoing therapies (physical therapy (PT), occupational therapy (OT), speech therapy (ST), feeding therapy (FT))
- Procedural elements:
  - Physical exam: Vital signs – temperature, systolic and diastolic blood pressures (mmHg), heart rate (beats/minute), respiratory rate (breaths/minute), Growth Data\* - length/height (cm), weight (kg), head circumference (HC in cm), Exam by systems – (normal/abnormal) brief neurologic exam, cardiovascular exam,

- abdominal exam, (HEENT) head ears eyes nose throat exam, dermatologic exam, pulmonary exam, musculoskeletal exam
- Mini-ICARS
- PATA
- NPCRS
- Blood collection\*\* (CBC (WBC, Hgb, Hct, Plt, % Neutrophils, % Lymphocytes, % Eosinophils, % Basophils, % Monocytes, % Bands, MCV, MCHC, MCH), electrolytes (Na, K, Cl, CO2), VBG (pH, pCO2, PO2, CO2, Base excess) or bicarbonate/CO2, liver function tests (AST, ALT, GGT, indirect and direct bilirubin, total protein, albumin, alkaline phosphatase, calcium, phosphorus, vitamin D, parathyroid hormone), coagulation factors (prothrombin time, coagulation factor XI, and antithrombin) kidney function tests (BUN, Creatinine), CTX, BSAP
- Urine collection (Urinalysis, urine calcium/creatinine ratio, urine protein/creatinine ratio, HCG for females)
- Survey given to families to complete and returned to site at or after visit by mail or electronically
  - PROMIS
- Performed after visit once inclusion and exclusion criteria are met and Mini-ICARS score established
  - Randomization

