## 6.2 Visit 2 (Remote)– Week 2-3

- Procedural elements
  - Blood collection (CBC, electrolytes and/or VBG, liver function tests, kidney function tests)
  - Urine collection (same as section 6.1)
- Medication adherence questionnaire (appendix E): family to send this to us electronically or via mail.
- Interview elements
  - AE assessment
  - Concomitant medication review
  - Ongoing therapies (same as section 6.1)
- Dose Adjustment (see section 5.2) – After venous blood gas and electrolytes have resulted, partnering clinician will instruct patient/caregiver regarding administration of drug or placebo via phone call, telehealth, or in person.

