## 8 Safety and Adverse Events

Blood will be collected at regular intervals to assess electrolytes level, kidney function, coagulation factor, and measure of base. Urine will also be collected at regular intervals to assess calcium and protein levels. Routine urinalysis will also be performed to monitor for any significant changes in body fluids as a result of acetazolamide function. Monitoring for thrombocytopenia, electrolyte disturbances, and metabolic acidosis should be completed within 4 weeks of a dose increase. If significant changes occur in blood or urine tests, risk will be re-evaluated by the principal investigator to determine if acetazolamide should be continued as per below. The AE reporting period will encompass visits 0 to 9 of the study. If a subject withdraws early, we will attempt to assess AEs up to 91 weeks after enrollment through review of medical records.

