### **Abnormal Laboratory Values**

A clinical laboratory abnormality should be documented as an adverse event if they meet the following criteria:

- Hepatic impairment defined as AST/ALT  $>3.0 - 5.0 \times$  ULN if baseline was normal;  $>3.0 - 5.0 \times$  baseline if baseline was abnormal
- Renal impairment defined as serum creatinine 1.5-1.9 times ULN for age OR  $\geq 26.5 \text{ umol/l}$  increase from ULN for age

If these values are noted and no other cause for these laboratory changes are likely, then drug will be stopped, and repeat labs will be obtained at reasonable intervals per investigator's clinical judgement after discontinuation until labs have normalized to stabilized. Treatment may be restarted if labs have returned to baseline using the same ramp up schedule as described for visits 2, 3 and 4. These changes in treatment will be documented.

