#### **10.1.3 Trial Safety**

See section 8 for description of any specific events that would preclude a subject from continuing the intervention and managing any medication related issues. See section 1.5 for potential risks and measures in place to protect subjects against foreseeable risks. Consent and assent procedures are described in section 11 below. Individuals will be consented or assented in person face to face. Subject privacy will be protected by the following measures - interviews will take place in a private room, testing data will be shared with subject's legally authorized representative, privacy for minors, communication between investigators and subject will be performed via secure means including via secure telephone, web portal, telehealth software. Trial stopping rules are described in section 8.5. Incidental findings will be reported to the subject and their parent/legal guardian, or legally authorized representative as well as their clinical provider. Decisions regarding management of these incidental findings will be deferred to the subject's clinical provider and family. Any conflicts of interest will be disclosed as per section 12.2. As a multi-center study, compliance with the monitoring plan will be ensured by the site PI, and data will be reported across study sites electronically. Additionally, all study related data will be collected in a centralized database as per section 9. Data security measures to protect the confidentiality of the data are also described in section 9.

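### Section 1.5 says all listed side effects are followed by history and laboratory studies, but no scheduled panel includes blood glucose or serum uric acid, so asymptomatic hyperglycemia, hypoglycemia and hyperuricemia have no blood test

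*Combined protocol and SAP*

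**What the plan says.** Section 1.5 (Risks) gives two lists. The first covers severe reactions and is followed by the laboratory tests to be monitored: CBC, liver tests, blood gas or bicarbonate, electrolytes, creatinine, and urinalysis with urine creatinine, calcium and protein. The second covers less severe effects, including hyperglycemia, hypoglycemia and hyperuricemia, and ends: "These symptoms are also all monitored during each visit by history and laboratory studies".

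The panels are itemised elsewhere. Section 3.7 has "electrolytes (Na, K, Cl, CO2), VBG (pH, pCO2, PO2, CO2, Base excess) or bicarbonate/CO2", plus liver, coagulation, kidney and bone-mineral items. The Visit 1 blood list in 6.1 ends with "kidney function tests (BUN, Creatinine), CTX, BSAP". The shorter Visit 2 list in 6.2 reads "Blood collection (CBC, electrolytes and/or VBG, liver function tests, kidney function tests".

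Section 10.1.3 sends the reader back to 1.5: "See section 1.5 for potential risks and measures in place to protect subjects against foreseeable risks". Section 8 adds: "If significant changes occur in blood or urine tests, risk will be re-evaluated by the principal investigator".

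**The concern.** The sponsor names changes in blood glucose and uric acid as possible drug effects, and section 1.5 reads as though laboratory work covers them where history cannot. The scheduled tests do not include either analyte. A subject with a silent change would not be identified, and the re-evaluation in section 8 cannot be triggered by a value that is never obtained.

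History is also a weaker tool in this trial than in most. Subjects may be as young as 4 years, the disease includes developmental delay and intellectual disability (section 1.1), and Visits 2 to 4 and 6 to 8 are remote.

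What is at stake is safety detection. Objective 2 commits to following laboratory values that the drug is likely to affect, and section 7.2 summarises drug-related adverse events from grade 1 upward. Silent changes in glucose or uric acid cannot enter that summary if they are not measured.

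**Working it through.** The plan gives no figure to reproduce; the check compares lists.

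**Step 1: the effects.** The second list in section 1.5 has 40 entries. Counting as blood-defined those that are themselves an abnormal blood value (my classification; jaundice and hemolysis are left out, though bilirubin and CBC are collected) gives 9.

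| Listed effect | Matching blood test in 3.7, 6.1 and 6.2 |
|---|---|
| Elevated hepatic enzymes | AST, ALT, GGT, alkaline phosphatase |
| Thrombocytopenia | Platelets (CBC) |
| Leukopenia | WBC (CBC) |
| Hyperchloremia | Cl |
| Hyponatremia | Na |
| Hypokalemia | K |
| Hyperglycemia | None |
| Hypoglycemia | None |
| Hyperuricemia | None |

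Matched: 6. Unmatched: 9 − 6 = 3, from two analytes. Section 6.2 allows a blood gas in place of electrolytes, so the three electrolyte effects are matched in the list rather than guaranteed at every visit.

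**Step 2: the visits.** Sections 6.3, 6.4, 6.6, 6.7 and 6.8 reuse the 6.2 blood list. Sections 6.5, 6.9 and 6.10 reuse the 6.1 list, and Visit 5 adds only an acetazolamide level. Glucose and uric acid are therefore specified at 0 of 9 visits: not at baseline, and at 0 of the 8 visits after it. Visit 1 precedes dosing, so the 8 later visits are the base for monitoring a drug effect.

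**Step 3: urine.** Urine is collected at Visits 1, 2, 3, 5, 6, 7 and 9, which is 7 of 9 overall and 7 − 1 = 6 of the 8 post-baseline visits. Sections 6.4 and 6.8 and Table 3 omit it at Visits 4 and 8. If the urinalysis reports glucose (an assumption), marked hyperglycemia could appear as glycosuria. Hypoglycemia could not, and serum uric acid is not measured.

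**Step 4: what the fix adds.**
- Maximum per subject: 2 assays × 9 draws = 18.
- If a subject who declines the extension has no draw after Visit 5: 2 × 5 = 10. Section 6 does not restrict later blood collection to those who continue, and the shading in Table 3 that would settle this is not visible in the copy reviewed, so 10 to 18 is the range for subjects who reach Visit 5.
- Ceiling for the trial: 18 × 33 = 594 at maximum accrual (section 3.2), or 18 × 26 = 468 for 26 subjects.
- Table 3 as read shows no blood mark at Visit 9, although 6.9 schedules it. On 8 draws the ceiling would be 2 × 8 × 33 = 528.

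**The case against.** The strongest reply is that the 1.5 sentence does not promise a blood test for each effect. Tinnitus and dysgeusia have no laboratory test, so history and laboratory studies must be meant jointly. The concrete laboratory commitment earlier in 1.5 claims neither analyte and agrees with section 6. Section 10.1.3 points to 1.5 as a whole, not to this sentence. On that view only the wording is loose. The reading of the sentence is right. It does not close the gap, because asymptomatic hyperuricemia or a mild glucose change is a laboratory finding that no history can establish.

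Other parts of the reply also stand. Urinalysis and questioning about crystalluria, nephrolithiasis and polyuria give some indirect cover. Section 8.2 requires specific questioning at each contact. Section 4.2 excludes users of antidiabetic agents. The protocol calls these effects less severe and gives no incidence for them. The section 1.4 table entry for the earlier open-label study in PMM2-CDG lists low bicarbonate, asthenia and paresthesia but no glucose or uric acid event, although it does not say whether these were measured.

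A reader might infer three stronger things that the documents do not support:
- *That the missing urine at Visits 4 and 8 breaks the rule on monitoring after a dose increase.* That rule is "Monitoring for thrombocytopenia, electrolyte disturbances, and metabolic acidosis should be completed within 4 weeks of a dose increase", and the blood draws serve it. Section 5.2 does not use urine for dosing.
- *That an abnormal value would automatically have become an adverse event.* Section 8.1 says "A clinical laboratory abnormality should be documented as an adverse event if they meet the following criteria" and then names only AST/ALT and creatinine. Glucose or uric acid would enter through 8.2, if judged clinically significant, and the modified grading criteria in Appendix D are not available here.
- *That these values will never be seen.* A local chemistry panel may report glucose, and 6.10 mentions serum chemistries from medical records after withdrawal. Neither is a scheduled study test.

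**Conclusion.** The point holds as a minor gap in safety monitoring. Three listed effects, resting on two analytes, have no scheduled blood test at baseline or at any of the 8 post-baseline visits, and urine at 6 of those 8 is a partial and indirect substitute. The conclusion about blood tests rests on the itemised panels meaning what they list. The credit given to urine assumes that the urinalysis reports glucose. The share of 3 in 9 depends on the classification in step 1, but the absence of the two tests does not.

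The documents do not show that subjects would be harmed or that such changes are frequent. Symptomatic events would still be sought. The primary analysis and sample size are unaffected. The change is worth making because it improves detection of effects the sponsor itself names, at low cost and without a new sample.

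**What to change.** 1. Add glucose and uric acid to the blood lists in 3.7, 6.1 and 6.2, on samples already drawn. Visits 3 to 9, early termination and the Table 3 footnote refer back to those sections and need no separate edit.
2. In the blinded phase, have the clinician outside the study who already monitors laboratory markers (5.2) review both results and pass on clinically significant values to be recorded as adverse events. One added sentence in 5.2 is enough.
3. Reword the 1.5 sentence to state which effects are followed by laboratory test and which by history only, and that urine is not collected at Visits 4 and 8. Adding urine at those visits is not required by section 8.

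The cost is two assays per scheduled draw: at most 18 per subject, fewer for those who do not enter the extension if their later draws lapse, and no more than 594 in total. No visit or blood sample is added. Some incidental abnormal values will need follow-up. A significant value passed to the investigator could hint at the arm, as any drug-related adverse event can.
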